**On Cycle 1, Day 1, the following procedures will be completed prior to first dose of protocol-indicated treatment:**

- Vital Signs: Heart rate (HR), blood pressure (BP), and temperature.
- Weight.
- Concomitant medication and Adverse Event review.
- Serum or urine Pregnancy Test in women of childbearing potential (as defined in [Appendix 4](#)) – unless serum pregnancy test during screening was previously completed ≤ 72 hours prior to a patient's first dose of protocol-indicated treatment.
- Peripheral blood sample for correlative research.

**On Cycle 1, Day 1, the following procedures will be completed in association with Arm A dosing:**

- Pre-Dose Vital Signs (≤30 minutes prior to START of nivolumab infusion):
  - Heart rate (HR), blood pressure (BP), and temperature.
- Nivolumab infusion:
  - On Cycle 1, Day 1, all patients in Arm A are scheduled to receive nivolumab as a 30 minute ( $\pm 10$  minutes) intravenous infusion.
- Post-Dose Vital Signs (≤30 minutes after the END of the nivolumab infusion):
  - Heart rate (HR), blood pressure (BP), and temperature.
- Relatlimab infusion:
  - On Cycles 1, Day 1, all patients in Arm A are scheduled to receive relatlimab as

---

- a 60 minute ( $\pm 10$  minutes) intravenous infusion.
- Note: Nivolumab and relatlimab are to be administered as SEPARATE intravenous treatments. On days when both drugs are administered (i.e. scheduled for Day 1 of each cycle), the nivolumab infusion must be completed BEFORE initiation of intravenous relatlimab – see [Section 9.6](#).
- Post-Dose Vital Signs ( $\leq 30$  minutes after the END of relatlimab):
  - Heart rate (HR), blood pressure (BP), and temperature.

## **7.7. Additional Assessments, Arm A: Cycle 1, Day 15**

**On Day 15 of Cycle 1, the following additional items will be completed for patients in Arm A:**

- Troponin-I.
- 12-lead ECG (single recording on local equipment), with additional ECGs as clinically indicated, per patient's study physician.
- Peripheral blood sample for correlative research.

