## 7.2. Study Calendar: Treatment Arm A

Tests and Procedures	Protocol Section	TREATMENT: ARM A: MHC-II (+)		Comments: Arm A All Cycles = 28 days (4 weeks) per cycle	
		4 week cycles			
		CYCLES 1+	CYCLES 1 & 2		
		Day 1 (+1-3d) 	Day 15		
Physical exam, weight 	8.4	X			
Vital Signs 	8.3	X		Heart rate, blood pressure and temperature (oral or tympanic).	
ECOG perform. status 	A2	X			
Review AEs 	8.5 & 11	X		Dose Holds: Section 11. AE reporting: Section 13.	
Review con meds 	8.5 & 10.2	X		Prohibited medications: Section 10.2.	
Hematology 	8.6	X		CBC w/ Diff.	
Serum chemistries 	8.7	X		CMP; Mg, Phos.	
Additional Labs 	8.8	X		LDH, TSH + reflexive (free T3 & free T4), cortisol, CK, and CK-MB.	
		X		If clinically indicated: ACTH, amylase and lipase.	
		c1d1 & c2d1	c1d15 & c2d15	Troponin-I	
Pregnancy test 	8.10	c1d1		Serum or urine (in WOCBP) ≤72hr prior to start of c1d1 tx. Contraception per Appendix 4.	
12-lead ECG 	8.9	c1d1 & c2d1	c1d15 & c2d15	Single tracing on local machine.	
CT or MRI 	8.11	q12 weeks (-1 to -7d) s/p c1d1		Re-scanning every 12 weeks (-1 to -7 days) after initiation of treatment on Cycle 1, Day 1.	
Fresh Tumor Biopsy	8.13		c2d15 (±7d)	(i.e. 6wk s/p c1d1)	
Peripheral blood sample 	8.14	c1d1, c4d1, & c14d1	c1d15 & c2d15	For correlative research. Kits required for collection. (Note: c4d1 & c14d1 are s/p 13 & 53 weeks after c1d1 Arm A tx.)	
TREATMENT: ARM A					
Nivolumab 	9.3	X		30min i.v. infusion: 480mg q4wk (on d1 of Cycles 1+).	
Relatlimab 	9.4	X		60min i.v. infusion: 160mg q4wk (on d1 of Cycles 1+). Relatlimab infusion started AFTER completion of nivolumab infusion.	

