### 7.3. Study Calendar: Treatment Arm B

Tests and Procedures	Protocol Section	TREATMENT: ARM B: MHC-II (-)						Comments: Arm B Cycles 1-4 = 21 days (3 weeks) per cycle Cycles 5+ = 28 days (4 weeks) per cycle	
		3 week cycles			4 week cycles				
		CYCLE 1		CYCLES 2, 3 & 4		CYCLES 5+			
		Day 1	Day 8	Day 15	Day 1 (+1-3d) 	Day 1 (+1-3d) 	Day 1 (+1-3d) 		
Physical exam, Weight 	8.4	X	X	X	X	X			
Vital Signs 	8.3	X	X	X	X	X		Heart rate, blood pressure and temperature (oral or tympanic).	
ECOG perform. status 	A2	X	X	X	X	X			
Review AEs 	8.5 & 11	X	X	X	X	X		Dose Holds: Section 11 . AE reporting: Section 13 .	
Review con meds 	8.5 & 10.2	X	X	X	X	X		Prohibited medications: Section 10.2 .	
Hematology 	8.6	X	X	X	X	X		CBC w/ Diff.	
Serum chemistries 	8.7	X	X	X	X	X		CMP; Mg, Phos.	
Additional Labs 	8.8	X	X	X	X	X		LDH, TSH + reflexive (free T3 & free T4). If clinically indicated: ACTH, amylase and lipase.	
		X	X	X	c2d1			Cortisol, troponin-I, CK, CK-MB.	
Pregnancy test 	8.10	X						Serum or urine (in WOCBP) ≤72hr prior to start of c1d1 tx. Contraception per Appendix 4 .	
CT or MRI 	8.11				q12 weeks (-1 to -7d) s/p c1d1			Re-scanning every 12 weeks (-1 to -7 days) after initiation of treatment on Cycle 1, Day 1.	
Fresh Tumor Biopsy	8.13				c3d1 ±7 days			(i.e. 6wk s/p c1d1)	
Peripheral blood sample 	8.14	X		X	c3d1	c5d1 & c15d1		For correlative research. Kits required for collection. (Note: c5d1 & c15d1 are s/p 13 and 53 Weeks of Arm B tx.)	
TREATMENT: ARM B									
Nivolumab 	9.3	X			X	X		30min i.v. infusion: 1mg/kg q3wk (on d1 of Cycles 1-4), then 480mg q4wk (on d1 of Cycles 5+).	
Ipilimumab 	9.5	X			X			90min i.v. infusion: 3mg/kg q3wk (on d1 of Cycles 1-4). Ipilimumab infusion started AFTER completion of nivolumab infusion.	

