**On Cycles 2+, Day 1, the following procedures will be completed prior to protocol-indicated treatment:**

- Physical Exam.
- Weight
- Vital Signs: Heart rate (HR), blood pressure (BP), and temperature.
- ECOG performance status.
- Concomitant medication and Adverse Event review.
- Complete Blood Count (CBC) with differential (including white blood cell count with differential, hemoglobin, hematocrit, and platelet count).
- Blood Chemistry [including sodium, potassium, chloride, bicarbonate or carbon dioxide, blood urea nitrogen (BUN), creatinine, glucose, total bilirubin, AST, ALT, alkaline phosphatase (ALP), calcium, albumin, total protein; magnesium and phosphorus].
- Additional labs: LDH, TSH (and if TSH is abnormal, then free T3 and free T4), cortisol, CK, and CK-MB. If clinically indicated: ACTH, amylase and lipase.

---

**On the days indicated below, the following additional items will be also be completed (prior to any protocol-indicated treatment):**

- Cycle 2, Day 1:
  - Troponin-I.
  - 12-lead ECG (single recording on local equipment), with additional ECGs as clinically indicated, per patient's study physician.
- Cycle 4, Day 1:
  - Peripheral blood sample for correlative research.
- Cycle 14, Day 1:
  - Peripheral blood sample for correlative research.

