## **7.9. Additional Assessments, Arm A: Cycle 2, Day 15**

**On Day 15 of Cycle 2, the following additional items will be completed for patients in Arm A:**

- Troponin-I.
- 12-lead ECG (single recording on local equipment), with additional ECGs as clinically indicated, per patient's study physician.
- Peripheral blood sample for correlative research.
- Fresh tumor biopsy ( $\pm$ 7 days).

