### **7.11. Assessments, Arm B: Cycle 1, Day 8 and Day 15**

**On Cycle 1, Day 8 and Day 15, the following procedures will be completed:**

- Physical Exam.
- Weight
- Vital Signs: Heart rate (HR), blood pressure (BP), and temperature.
- ECOG performance status.
- Concomitant medication and Adverse Event review.
- Complete Blood Count (CBC) with differential (including white blood cell count with differential, hemoglobin, hematocrit, and platelet count).
- Blood Chemistry [including sodium, potassium, chloride, bicarbonate or carbon dioxide, blood urea nitrogen (BUN), creatinine, glucose, total bilirubin, AST, ALT, alkaline phosphatase (ALP), calcium, albumin, total protein; magnesium and phosphorus].
- Additional labs: LDH, TSH (and if TSH is abnormal, then free T3 and free T4), cortisol, troponin-I, CK, and CK-MB. If clinically indicated: ACTH, amylase and lipase.

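### Scheduled review of adverse events and concomitant medication is half as frequent in Arm A as in Arm B over the first 12 weeks, partly because the Arm A Day 15 contacts omit it

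*Combined protocol and SAP*

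**What the plan says.** **Arm A.** The calendar in Section 7.2 sets "All Cycles = 28 days (4 weeks) per cycle". Its adverse-event row, annotated "Dose Holds: Section 11. AE reporting: Section 13", and its concomitant-medication row are marked under Day 1 only; the Day 15 cells are blank. The text agrees. Section 7.7 ("On Day 15 of Cycle 1, the following additional items will be completed for patients in Arm A") lists troponin-I, a 12-lead ECG and research blood. Section 7.9 ("On Day 15 of Cycle 2, the following additional items will be completed for patients in Arm A") lists the same three items plus the fresh biopsy. The reviews appear in Section 7.8 under "On Cycles 2+, Day 1, the following procedures will be completed prior to protocol-indicated treatment".

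**Arm B.** The calendar in Section 7.3 sets "Cycles 1-4 = 21 days (3 weeks) per cycle". Section 7.11 ("On Cycle 1, Day 8 and Day 15, the following procedures will be completed") includes "Concomitant medication and Adverse Event review", along with examination, vital signs, blood count and chemistry. Section 7.12 repeats the review on Day 1 of Cycles 2 to 4, and Section 7.13 from Cycle 5 on.

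**Both arms.** Section 4 makes adverse events a secondary endpoint. Section 8.5 ties medication review to the visits marked in Section 7 and refers adverse events to Section 13. Section 13.1 collects adverse events from the first dose until 100 days after the last dose, or until another anticancer therapy starts if that is sooner.

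**The concern.** How often patients are asked affects how many mild and short-lived events are recorded, and how accurately they are dated. After the first dose, the first scheduled question about adverse events comes on Day 29 in Arm A and on Day 8 in Arm B. An Arm A event that starts and resolves within Cycle 1 reaches the database through the patient's own report, an incidental finding, or recall on Day 29.

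Low-grade events are the bulk of what is expected. In the relatlimab plus nivolumab data in Table 2 (Section 3.3), 157 of 304 subjects had a drug-related event, 31 had Grade 3-4 and 1 had Grade 5. At least 157 - 31 - 1 = 125 of the 157 (80%) therefore had nothing above Grade 2.

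The direction is also predictable: less frequent asking can make Arm A look somewhat better tolerated when the two safety tables are read side by side. In addition, Arm A has no scheduled medication review at the week-6 biopsy that supplies the primary endpoint. Steroid exposure at that point bears on the reading of the T-cell density.

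**Working it through.** **Inputs.** Cycle lengths and marked visits come from Sections 7.2, 7.3, 7.7 to 7.9 and 7.11 to 7.13. All days are nominal, with Cycle 1, Day 1 as Day 1; administrative windows and delays are ignored.

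**Visit-day formulas** (c = cycle, d = day of cycle)
- Arm A: 28(c - 1) + d
- Arm B, Cycles 1 to 4: 21(c - 1) + d
- Arm B, Cycle 5 on: 84 + 28(c - 5) + d

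**Check against the plan's own figure.** The documents give no count of reviews. Section 8.13 places both biopsies about 6 weeks after the start of treatment. Arm A, Cycle 2, Day 15: 28 + 15 = Day 43. Arm B, Cycle 3, Day 1: 42 + 1 = Day 43. Both are 42 days, or 6 weeks, after Day 1, so the formulas reproduce the stated timing.

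**Scheduled reviews after the first dose, through Day 85**
- Arm A: Days 29, 57, 85 = 3
- Arm B: Days 8, 15, 22, 43, 64, 85 = 6
- Ratio: 3/6 = 0.50

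Before Day 29 the count is 0 in Arm A and 3 in Arm B (Days 8, 15, 22). From Day 85 both arms follow the same 28-day pattern, so the imbalance is confined to the first 12 weeks.

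**Where the difference of 3 comes from.** Day 1 visits alone give 3 in Arm A and 4 in Arm B (Days 22, 43, 64, 85), so cycle length accounts for 1. The Arm B reviews at Cycle 1, Days 8 and 15 account for the other 2. Arm A has two contacts of its own in this period, on Days 15 and 43, without a review.

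**Effect of adding the two Arm A reviews**

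| Period after first dose | Arm A now | Arm A with Day 15 reviews | Arm B |
|---|---|---|---|
| Before Day 29 | 0 | 1 | 3 |
| Through Day 57 | 2 | 4 | 4 |
| Through Day 85 | 3 | 5 | 6 |

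Through Day 57 the longest Arm A interval between reviews falls from 28 days (1 to 29, 29 to 57) to 14 days (1, 15, 29, 43, 57). The interval from Day 57 to Day 85 stays at 28 days.

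**Other toxicity measures.** Scheduled troponin-I after the first dose is equal, at 3 each: Days 15, 29 and 43 in Arm A; Days 8, 15 and 22 in Arm B. On-treatment ECGs are scheduled only in Arm A. Cortisol, CK and CK-MB continue every cycle in Arm A but stop after Cycle 2, Day 1 in Arm B.

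**Biopsy.** With the ±7 day window, either arm's biopsy may fall anywhere from Day 36 to Day 50. The neighbouring Arm A medication reviews are on Days 29 and 57. Arm B has one on Day 43, but the biopsy need not be taken that day.

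**The case against.** A reader might infer that toxicity as a whole is measured half as often in Arm A. The documents do not support that: troponin counts are equal, and ECG and some enzyme monitoring is heavier in Arm A. The halving applies to scheduled review of events and medications.

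A reader might also infer that Arm A events go unrecorded. Section 13.1 requires events to be captured however they come to light, and Section 11 has patients told to report symptoms as soon as they appear. An event mentioned on Day 15 must already be recorded. Likewise, Section 10.1 requires medications to be recorded throughout participation and names corticosteroids, so steroid use before the Arm A biopsy is already required data. The biopsy contrast between arms is also weaker than it looks, because the window is the same in both.

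Nor is a biased formal comparison of safety established. Section 3.7 says the arms are evaluated in parallel and not compared, and Section 18.3 states safety by regimen. The chi-squared and Fisher tests in Section 18.4 are generic and do not name adverse events. Assignment by MHC-II status confounds any contrast in any case.

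Finally, closer early review of the more toxic regimen is a defensible choice. The protocol cites 59% Grade 3-4 treatment-related events for nivolumab plus ipilimumab (Section 3.2), against 10.2% (Section 3.3) and 13.9% (Section 13.3) for nivolumab plus relatlimab.

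All of this limits the harm. It does not explain why two contacts that Arm A patients already attend should pass without the question, and by-arm safety tables will be read next to each other whatever the stated intent.

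**Conclusion.** The point holds for scheduled review: 3 against 6 after the first dose through Day 85, and 0 against 3 before Day 29. The cause is partly the 28- against 21-day cycles and partly the absence of review at Arm A's Cycle 1 and Cycle 2 Day 15 contacts. The consequence is that mild or transient Arm A events are sought less actively and less promptly. That may lower their recorded incidence and blur onset dates; it does not mean events are lost by design.

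The size of any effect on recorded rates cannot be derived from the documents, which give no event durations or detection probabilities. A firm statement that Arm A incidence is lowered would go too far. The counts rest on nominal visit days and on reading the blank calendar cells as intended, which the lists in Sections 7.7 and 7.9 confirm. This is a worthwhile, low-cost improvement in the collection of a secondary endpoint; it does not undermine the primary analysis.

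**What to change.** 1. In Sections 7.2, 7.7 and 7.9, add adverse-event review and concomitant-medication review at Cycle 1, Day 15 and Cycle 2, Day 15 for Arm A.
2. In both arms, record systemic corticosteroid or other immunosuppressant use on the actual day of the week-6 biopsy, since the window means it may not fall on a review visit.
3. State in the safety summary that scheduled review frequency still differs by arm: 5 against 6 through Day 85, and 1 against 3 before Day 29.

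The cost is a few minutes and slightly more data entry at two existing contacts per Arm A patient, with no new visit. This assumes that someone able to take an adverse-event history is available at those contacts; the documents do not say who staffs them. The change concerns data collection only and alters no dose, hold or stopping rule.

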## **7.8. Assessments, Arm A: Cycles 2+, Day 1**

Beginning with Cycle 2, Day 1: Up to 3 days delay (i.e. plus 1 to 3 days; but not minus 1 to 3 days) in the initiation of Day 1 of a new cycle, will be permitted in order to facilitate holidays, weekends, bad weather, scheduling, or other unforeseen circumstances not including adverse events. Such administrative delay – not to be used for adverse event management – will not be considered a protocol deviation.

Also, in order to facilitate scheduling flexibility for on-study laboratory items: For all cycles, beginning with Cycle 2, Day 1: Laboratories designated as Hematology, Serum Chemistries or as "Additional Labs" in Section 7.2 (Arm A) need not be repeated on days of treatment, if already resulted  $\leq 3$  days prior to treatment.

**On Cycles 2+, Day 1, the following procedures will be completed prior to protocol-indicated treatment:**

- Physical Exam.
- Weight
- Vital Signs: Heart rate (HR), blood pressure (BP), and temperature.
- ECOG performance status.
- Concomitant medication and Adverse Event review.
- Complete Blood Count (CBC) with differential (including white blood cell count with differential, hemoglobin, hematocrit, and platelet count).
- Blood Chemistry [including sodium, potassium, chloride, bicarbonate or carbon dioxide, blood urea nitrogen (BUN), creatinine, glucose, total bilirubin, AST, ALT, alkaline phosphatase (ALP), calcium, albumin, total protein; magnesium and phosphorus].
- Additional labs: LDH, TSH (and if TSH is abnormal, then free T3 and free T4), cortisol, CK, and CK-MB. If clinically indicated: ACTH, amylase and lipase.

---

**On the days indicated below, the following additional items will be also be completed (prior to any protocol-indicated treatment):**

- Cycle 2, Day 1:
  - Troponin-I.
  - 12-lead ECG (single recording on local equipment), with additional ECGs as clinically indicated, per patient's study physician.
- Cycle 4, Day 1:
  - Peripheral blood sample for correlative research.
- Cycle 14, Day 1:
  - Peripheral blood sample for correlative research.

**On Cycles 2+, Day 1, the following procedures will be completed in association with Arm A dosing:**

- Pre-Dose Vital Signs ( $\leq$ 30 minutes prior to START of nivolumab infusion):
  - Heart rate (HR), blood pressure (BP), and temperature.
- Nivolumab infusion:
  - On Cycles 2+, Day 1, all patients in Arm A are scheduled to receive nivolumab as a 30 minute ( $\pm$ 10 minutes) intravenous infusion.
- Post-Dose Vital Signs ( $\leq$ 30 minutes after the END of the nivolumab infusion):
  - Heart rate (HR), blood pressure (BP), and temperature.
- Relatlimab infusion:
  - On Cycles 2+, Day 1, all patients in Arm A are scheduled to receive relatlimab as a 60 minute ( $\pm$ 10 minutes) intravenous infusion.
  - Note: Nivolumab and relatlimab are to be administered as SEPARATE intravenous treatments. On days when both drugs are administered (i.e. scheduled for Day 1 of each cycle), the nivolumab infusion must be completed BEFORE initiation of intravenous relatlimab – see [Section 9.6](#).
- Post-Dose Vital Signs ( $\leq$ 30 minutes after the END of relatlimab):
  - Heart rate (HR), blood pressure (BP), and temperature.

## **7.9. Additional Assessments, Arm A: Cycle 2, Day 15**

**On Day 15 of Cycle 2, the following additional items will be completed for patients in Arm A:**

- Troponin-I.
- 12-lead ECG (single recording on local equipment), with additional ECGs as clinically indicated, per patient's study physician.
- Peripheral blood sample for correlative research.
- Fresh tumor biopsy ( $\pm$ 7 days).

## **7.10. Assessments, Arm B: Cycle 1, Day 1**

**On Cycle 1, Day 1, the following procedures must be completed, unless previously completed  $\leq$ 7 days prior to a patient's first dose of protocol-indicated treatment:**

- Physical Exam.
- ECOG performance status.
- Complete Blood Count (CBC) with differential (including white blood cell count with differential, hemoglobin, hematocrit, and platelet count).
- Blood Chemistry [including sodium, potassium, chloride, bicarbonate or carbon dioxide, blood urea nitrogen (BUN), creatinine, glucose, total bilirubin, AST, ALT, alkaline phosphatase (ALP), calcium, albumin, total protein; magnesium and phosphorus].
- Additional labs: LDH, TSH (and if TSH is abnormal, then free T3 and free T4), cortisol, CK, CK-MB, and troponin-I. If clinically indicated: ACTH, amylase and lipase.

**On Cycle 1, Day 1, the following procedures will be completed prior to first dose of protocol-indicated treatment:**

- Vital Signs: Heart rate (HR), blood pressure (BP), and temperature.
- Weight.
- Concomitant medication and Adverse Event review.
- Serum or urine Pregnancy Test in women of childbearing potential (as defined in [Appendix 4](#)) – unless serum pregnancy test during screening was previously completed ≤ 72 hours prior to a patient's first dose of protocol-indicated treatment.
- Peripheral blood sample for correlative research.

**On Cycle 1, Day 1, the following procedures will be completed in association with Arm B dosing:**

- Pre-Dose Vital Signs (≤30 minutes prior to START of nivolumab infusion):
  - Heart rate (HR), blood pressure (BP), and temperature.
- Nivolumab infusion:
  - On Cycle 1, Day 1, all patients in Arm B are scheduled to receive nivolumab as a 30 minute (±10 minutes) intravenous infusion.
- Post-Dose Vital Signs (≤30 minutes after the END of the nivolumab infusion):
  - Heart rate (HR), blood pressure (BP), and temperature.
- Ipilimumab infusion:
  - On Cycle 1, Day 1, all patients in Arm B are scheduled to receive ipilimumab as a 90 minute (±10 minutes) intravenous infusion.
  - Note: Nivolumab and ipilimumab are to be administered as SEPARATE intravenous treatments. On days when both drugs are administered, the nivolumab infusion must be completed BEFORE initiation of intravenous ipilimumab – see [Section 9.7](#).
- Post-Dose Vital Signs (≤30 minutes after the END of ipilimumab):
  - Heart rate (HR), blood pressure (BP), and temperature.

### **7.11. Assessments, Arm B: Cycle 1, Day 8 and Day 15**

**On Cycle 1, Day 8 and Day 15, the following procedures will be completed:**

- Physical Exam.
- Weight
- Vital Signs: Heart rate (HR), blood pressure (BP), and temperature.
- ECOG performance status.
- Concomitant medication and Adverse Event review.
- Complete Blood Count (CBC) with differential (including white blood cell count with differential, hemoglobin, hematocrit, and platelet count).
- Blood Chemistry [including sodium, potassium, chloride, bicarbonate or carbon dioxide, blood urea nitrogen (BUN), creatinine, glucose, total bilirubin, AST, ALT, alkaline phosphatase (ALP), calcium, albumin, total protein; magnesium and phosphorus].
- Additional labs: LDH, TSH (and if TSH is abnormal, then free T3 and free T4), cortisol, troponin-I, CK, and CK-MB. If clinically indicated: ACTH, amylase and lipase.

**On Cycle 1, Day 15, the following will also be completed:**

- Peripheral blood sample for correlative research.

### **7.12. Assessments, Arm B: Cycles 2-4, Day 1**

Beginning with Cycle 2, Day 1: Up to 3 days delay (i.e. plus 1 to 3 days; but not minus 1 to 3 days) in the initiation of Day 1 of a new cycle, will be permitted in order to facilitate holidays, weekends, bad weather, scheduling, or other unforeseen circumstances not including adverse events. Such administrative delay – not to be used for adverse event management – will not be considered a protocol deviation.

Also, in order to facilitate scheduling flexibility for on-study laboratory items: For all cycles, beginning with Cycle 2, Day 1: Laboratories designated as Hematology, Serum Chemistries or as “Additional Labs” in Section 7.3 (Arm B) need not be repeated on days of treatment, if already resulted  $\leq$  3 days prior to treatment.

